#### **6.12. Resistance Surveillance and ddPCR**

Sequence analysis of the HBV polymerase/reverse transcriptase (pol/RT) to assess the incidence of resistance mutations will be attempted for any subject with viremia (HBV DNA  $\geq 69$  IU/mL) at Week 48 or at early discontinuation at or after Week 24. As it may not be known at the time of the visit whether a subject is viremic or if it will be their last study visit, a separate virology sample for potential resistance surveillance will be collected at each study visit.

For Group 4, if subject has HBV DNA  $\geq 69$  IU/mL, a sequence analysis may be conducted if applicable. If HBV DNA  $< 20$  IU/mL, ddPCR will be conducted.

#### **6.13. End of Study**

The end of this study will be last subject's last observation.

Once a subject has completed their study participation, the long-term care of the participant will return to the responsibility of their primary treating physicians.

## 7. ADVERSE EVENTS AND TOXICITY MANAGEMENT

### 7.1. Definitions of Adverse Events, Adverse Reactions, and Serious Adverse Events

#### 7.1.1. Adverse Events

An adverse event (AE) is any untoward medical occurrence in a clinical study subject administered a medicinal product, which does not necessarily have a causal relationship with the treatment. An AE can therefore be any unfavorable and/or unintended sign, symptom, or disease temporally associated with the use of a medicinal product, whether or not considered related to the medicinal product. AEs may also include pre- or post-treatment complications that occur as a result of protocol specified procedures, lack of efficacy, overdose, drug abuse/misuse reports, or occupational exposure. Preexisting events that increase in severity or change in nature during or as a consequence of participation in the clinical study will also be considered AEs.

An AE does not include the following:

- Medical or surgical procedures such as surgery, endoscopy, tooth extraction, and transfusion. The condition that led to the procedure may be an adverse event and must be reported.
- Pre-existing diseases, conditions, or laboratory abnormalities present or detected before the screening visit that do not worsen
- Situations where an untoward medical occurrence has not occurred (e.g., hospitalization for elective surgery, social and/or convenience admissions)
- Overdose without clinical sequelae (see Section 7.7.1)
- Any medical condition or clinically significant laboratory abnormality with an onset date before the consent form is signed and not related to a protocol-associated procedure is not an AE. It is considered to be pre-existing and should be documented on the medical history eCRF.

#### 7.1.2. Serious Adverse Events

A **serious adverse event** (SAE) is defined as an event that, at any dose, results in the following:

- Death
- Life-threatening (Note: The term “life-threatening” in the definition of “serious” refers to an event in which the subject was at risk of death at the time of the event; it does not refer to an event that hypothetically might have caused death if it were more severe.)
- In-patient hospitalization or prolongation of existing hospitalization

- Persistent or significant disability/incapacity
- A congenital anomaly/birth defect
- A medically important event or reaction: such events may not be immediately life-threatening or result in death or hospitalization but may jeopardize the subject or may require intervention to prevent one of the other outcomes constituting SAEs. Medical and scientific judgment must be exercised to determine whether such an event is a reportable under expedited reporting rules. Examples of medically important events include intensive treatment in an emergency room or at home for allergic bronchospasm; blood dyscrasias or convulsions that do not result in hospitalization; and development of drug dependency or drug abuse. For the avoidance of doubt, infections resulting from contaminated medicinal product will be considered a medically important event and subject to expedited reporting requirements.

## **7.2. Assessment of Adverse Events and Serious Adverse Events**

The investigator or qualified subinvestigator is responsible for assessing AEs and SAEs for causality and severity, and for final review and confirmation of accuracy of event information and assessments.

### **7.2.1. Assessment of Causality for Study Drugs and Procedures**

The investigator or qualified subinvestigator is responsible for assessing the relationship to each IMP therapy using clinical judgment and the following considerations:

- **No:** Evidence exists that the adverse event has an etiology other than the IMP. For SAEs, an alternative causality must be provided (e.g., pre-existing condition, underlying disease, intercurrent illness, or concomitant medication).
- **Yes:** There is reasonable possibility that the event may have been caused by the investigational medicinal product.

It should be emphasized that ineffective treatment should not be considered as causally related in the context of adverse event reporting.

The relationship to study procedures (e.g., invasive procedures such as venipuncture or biopsy) should be assessed using the following considerations:

- **No:** Evidence exists that the adverse event has an etiology other than the study procedure.
- **Yes:** The adverse event occurred as a result of protocol procedures, (e.g., venipuncture)

### **7.2.2. Assessment of Severity**

Severity of adverse events is to be determined based on GSI Grading Scale for Severity of Adverse Events and Laboratory Abnormalities ([Appendix 3](#)). A distinction should be drawn between seriousness and severity of AEs. An AE that is assessed as Grade 4 (potentially life-threatening) should not be confused with an SAE. Severity is a category utilized for rating the intensity of an event: both AEs and SAEs can be assessed as Grade 4. An event is defined as “serious” when it meets one of the predefined outcomes described above in Section [7.1.2](#).

### **7.3. Investigator Requirements and Instructions for Reporting Adverse Events and Serious Adverse Events to Gilead**

Requirements for collection prior to study drug initiation:

After informed consent, but prior to initiation of study medication, the following types of events should be reported on the case report form (eCRF): all SAEs and adverse events related to protocol-mandated procedures.

#### **Adverse Events**

Following initiation of study medication, collect all AEs, regardless of cause or relationship, until 30 days after last administration of study IMP must be reported to the eCRF database as instructed.

All AEs should be followed up until resolution or until the adverse event is stable, if possible. Gilead Sciences may request that certain AEs be followed beyond the protocol defined follow up period.

#### **Serious Adverse Events**

All SAEs, regardless of cause or relationship, that occurs after the subject first consents to participate in the study (i.e., signing the informed consent) and throughout the duration of the study, including the protocol-required post treatment follow-up period, must be reported to the eCRF database and Gilead Pharmacovigilance and Epidemiology (PVE) as instructed. This also includes any SAEs resulting from protocol-associated procedures performed after informed consent is signed.

Investigators are not obligated to actively seek SAEs after the protocol defined follow up period; however, if the investigator learns of any SAEs that occur after study participation has concluded and the event is deemed relevant to the use of IMP, he/she should promptly document and report the event to Gilead PVE.

- All AEs and SAEs will be recorded in the eCRF database within the timelines outlined in the eCRF completion guideline.

### Electronic Serious Adverse Event (eSAE) Reporting Process

- Site personnel must record all SAE data in the eCRF database and transmit the SAE information to Gilead PVE within 24 hours of the investigator's knowledge of the event. Detailed instructions can be found in the eCRF completion guidelines.
- If it is not possible to record and submit the SAE information electronically, because the eCRF database cannot be accessed or is not available (including at study start), record the SAE on the paper serious adverse event report form and submit by e-mail or fax within 24 hours of the investigator's knowledge of the event to:

Gilead PVE:

Fax:

PPD

E-mail:

PPD

- As soon as it is possible to do so, any SAE reported via paper must be transcribed into the eCRF Database according to instructions in the eCRF completion guidelines.
- If an SAE has been reported via a paper form because the eCRF database has been locked, no further action is necessary.
- For fatal or life-threatening events, copies of hospital case reports, autopsy reports, and other documents are also to be submitted by e-mail or fax when requested and applicable. Transmission of such documents should occur without personal subject identification, maintaining the traceability of a document to the subject identifiers.
- Additional information may be requested to ensure the timely completion of accurate safety reports.
- Any medications necessary for treatment of the SAE must be recorded onto the concomitant medication section of the subject's eCRF and the event description section of the SAE form.

#### **7.4. Gilead Reporting Requirements**

Depending on relevant local legislation or regulations, including the applicable US FDA Code of Federal Regulations, the EU Clinical Trials Directive (2001/20/EC) and relevant updates, and other country-specific legislation or regulations, Gilead may be required to expedite to worldwide regulatory agencies reports of SAEs, serious adverse drug reactions (SADRs), or suspected unexpected serious adverse reactions (SUSARs). In accordance with the EU Clinical Trials Directive (2001/20/EC), Gilead or a specified designee will notify worldwide regulatory agencies and the relevant IEC in concerned Member States of applicable SUSARs as outlined in current regulations.

Assessment of expectedness for SAEs will be determined by Gilead using reference safety information specified in the Investigator's Brochure or relevant local label as applicable.

All investigators will receive a safety letter notifying them of relevant SUSAR reports associated with any study IMP. The investigator should notify the IRB or IEC of SUSAR reports as soon as is practical, where this is required by local regulatory agencies, and in accordance with the local institutional policy.

### **7.5. Clinical Laboratory Abnormalities and Other Abnormal Assessments as Adverse Events or Serious Adverse Events and Toxicity Management**

Laboratory abnormalities are usually not recorded as AEs or SAEs. However, laboratory abnormalities (e.g., clinical chemistry, hematology, and urinalysis) independent of the underlying medical condition that require medical or surgical intervention or lead to investigational medicinal product interruption or discontinuation must be recorded as an AE, as well as an SAE, if applicable. In addition, laboratory or other abnormal assessments (e.g., ECG, X-rays, and vital signs) that are associated with signs and/or symptoms must be recorded as an AE or SAE if they meet the definition of an AE (or SAE) as described in Sections 7.1.1 and 7.1.2. If the laboratory abnormality is part of a syndrome, record the syndrome or diagnosis (i.e., anemia) not the laboratory result (i.e., decreased hemoglobin).

Severity should be recorded and graded according to the GSI Grading Scale for Severity of Adverse Events and Laboratory Abnormalities ([Appendix 3](#)). For AEs associated with laboratory abnormalities, the event should be graded on the basis of the clinical severity in the context of the underlying conditions; this may or may not be in agreement with the grading of the laboratory abnormality.

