### Adverse Events by Severity

The majority of AEs reported in the TAF Phase 3 Safety Population were Grade 1 or 2. A similar percentage of subjects in each treatment group experienced at least 1 Grade 3 AE (TAF 4.5%, 39 subjects; TDF 3.9%, 17 subjects). No subjects in either group had a Grade 4 AE. The only Grade 3 AE that occurred in more than 2 subjects in either treatment group were increased ALT (TAF 0.6%, 5 subjects; TDF 0.7%, 3 subjects) and hepatocellular carcinoma (HCC) (TAF 0 subjects; TDF 0.7%, 3 subjects). Four Grade 3 ALT increases (TAF 3 subjects; TDF 1 subject) were assessed as related to study drug.

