**Table 7-1. GS-9992 Dose Modification and Monitoring**

Liver Toxicity	Action
Confirmed ALT $\geq 10 \times$ ULN without evidence of hepatic toxicity as defined below	Discuss with the Medical Monitor if GS-9992 should be dose reduced by 50% or discontinued if the safety of the subject is of immediate concern. Subject should be monitored weekly or more frequently if clinically indicated until ALT $< 5 \times$ ULN
Confirmed ALT $> 2 \times$ nadir, with evidence of hepatic toxicity, defined as any one of the following: 
 
• Total bilirubin <math>> 2 \times</math> baseline or nadir AND <math>> \text{ULN}</math> in the absence of Gilbert's disease
 
• Elevated INR <math>> 0.5</math> above baseline AND <math>> \text{ULN}</math>
 
• Abnormal serum albumin <math>> 1 \text{ g/dL}</math> decrease from baseline
 
	Permanently discontinue GS-9992. Subject should be monitored weekly until ALT $< 5 \times$ ULN, and total bilirubin and INR values return to normal or baseline levels
Confirmed ALT $> 2 \times$ Baseline and $\geq 5 \times$ ULN without evidence of hepatic toxicity, as defined above	Continue GS-9992, ALT should be evaluated every 2 weeks or more frequently as clinically needed, until ALT $< 5 \times$ ULN

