**Table 7-2. TAF Dose Modification and Monitoring**

Liver Toxicity	Action
Confirmed ALT levels $\geq 10 \times$ ULN, with evidence of hepatic toxicity, defined as any one of the following: 
 
• Total bilirubin <math>> 2 \times</math> baseline or nadir AND <math>> \text{ULN}</math> in the absence of Gilbert's disease
 
• Elevated INR <math>> 0.5</math> above baseline AND <math>> \text{ULN}</math>
 
• Abnormal serum albumin <math>> 1 \text{ g/dL}</math> decrease from baseline
 
	Discuss with the Medical Monitor if TAF should be discontinued, unless the safety of the subject is of immediate concern. Subject should be monitored weekly as long as ALT, total bilirubin and INR values remain elevated or above baseline values. If the ALT values remain persistently elevated, the investigator should discuss with the Medical Monitor if TAF should be discontinued.
Confirmed ALT levels $\geq 10 \times$ ULN, without evidence of hepatic toxicity, as defined above	Continue TAF and monitor weekly until ALT values return to normal or baseline levels. If the ALT values remain persistently elevated, the investigator should discuss with the Medical Monitor if TAF should be discontinued.

Specific toxicity discontinuation criteria in Section 6.11 supersede below general toxicity guidelines, and in general, where discrepancy is present, the more conservative criteria apply. The Gilead Medical Monitor should be consulted prior to study drug discontinuation when medically feasible.

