### **8.6.2. Adverse Events**

Clinical and laboratory adverse events (AEs) will be coded using the Medical Dictionary for Regulatory Activities (MedDRA). System Organ Class (SOC), High-Level Group Term (HLGT), High-Level Term (HLT), Preferred Term (PT), and Lower-Level Term (LLT) will be attached to the clinical database.

Summaries (number and percentage of subjects) of treatment-emergent (TE) AEs (by SOC and PT) will be provided by treatment group:

- All TEAEs
- TEAEs of Grade 3 or higher
- TEAEs of Grade 2 or higher
- All TE treatment-related AEs
- TE treatment-related AEs of Grade 3 or higher
- TE treatment-related AEs of Grade 2 or higher
- All TE SAEs
- All TE treatment-related SAEs
- All TEAEs leading to premature discontinuation of any study drug
- All TEAEs leading to temporary interruption of any study drug

All AEs collected during the study will be presented in the data listings.

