#### 7.1.6. Summaries of Adverse Events and Deaths

AEs will be summarized based on the Safety Analysis Set.

3 sets of summaries will be generated: (1) all TEAEs for 12 Week Regimen (2) all TEAEs for 48 Week Regimen (Group 1-3, and 5). (3) all AEs during TFFU period (AEs that occur during TFFU after Week 48) will be listed, and summary tables will be presented using the TFFU Analysis Set as appropriate.

A brief, high-level summary of the number and percentage of subjects who experienced at least 1 TEAE in the categories described below will be provided by treatment group. All deaths observed in the study will also be included in this summary.

The number and percentage of subjects who experienced at least 1 TEAE will be provided and summarized by SOC, PT and treatment group:

- TEAEs (with severity)

For the AE categories described below, summaries will be provided by PT and treatment group:

- TEAEs
- TEAEs of Grade 3 or higher
- TE treatment-related AEs
- GS-9992 only TE treatment-related AEs (Group 1, 3-5)
- TE treatment-related AEs of Grade 3 or higher
- TE SAEs
- TE treatment-related SAEs
- TEAEs leading to premature discontinuation of GS-9992
- TEAEs leading to premature discontinuation of TAF
- TEAEs leading to dose modification or temporary interruption of GS-9992
- TEAEs leading to dose modification or temporary interruption of TAF

Multiple events will be counted only once per subject in each summary. Adverse events will be summarized and listed first in alphabetic order by SOC and then by PT in descending order of total frequency within each SOC. For summaries by severity grade, the most severe grade will be used for those AEs that occurred more than once in an individual subject during the study.

In addition to the by-treatment summaries described above, data listings will be provided for the following AEs:

- All AEs, indicating whether the event is treatment-emergent
- All AEs of Grade 3 or higher
- SAEs
- All deaths
- AEs leading to premature discontinuation of any study drug
- AEs leading to dose modification or temporary interruption of any study drug

For subjects in the TFFU Analysis Set, by-subject listings will be provided as follows:

- All AEs
- AEs of Grade 3 or higher
- All SAEs
- All deaths

The listings will indicate whether an event is treatment-emergent, and whether the event occurred during TFFU.

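### Whether an ALT abnormality must be recorded as an AE depends in part on drug action, and the ALT action rules differ between GS-9992 and TAF, so ALT-related TEAE counts can differ by group for the same finding

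*Protocol*

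**What the plan says.** **Recording.** Protocol 7.5 starts from a default: "Laboratory abnormalities are usually not recorded as AEs or SAEs". It then gives three routes to an AE. Two share a sentence limited to abnormalities not explained by the underlying condition: those "that require medical or surgical intervention or lead to investigational medicinal product interruption or discontinuation must be recorded as an AE". The third covers abnormal assessments "that are associated with signs and/or symptoms must be recorded as an AE or SAE if they meet the definition of an AE". Dose reduction is not named as a route.

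**Drug action.** At confirmed ALT ≥10×ULN without hepatic toxicity, Table 7-1 says "Discuss with the Medical Monitor if GS-9992 should be dose reduced by 50% or discontinued", with the subject's immediate safety as the qualifier. For the same finding Table 7-2 says "Continue TAF and monitor weekly until ALT values return to normal or baseline levels", and discontinuation is raised only if the elevation persists. At confirmed ALT >2×nadir with hepatic toxicity (a bilirubin, INR or albumin criterion), Table 7-1 requires a permanent stop of GS-9992. Table 7-2 has stopping TAF discussed, and only from 10×ULN.

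**Reporting.** Protocol 8.6.2 tabulates all TEAEs, treatment-related TEAEs and "TEAEs of Grade 3 or higher" by treatment group. SAP 7.1.6 keeps these and adds "TEAEs leading to premature discontinuation of GS-9992". SAP 7.2.3.3 summarises graded laboratory abnormalities by group for the 12 Week Regimen from the laboratory values themselves. The liver and ALT-flare summary in SAP 7.2.4 is planned only for the Week 48 Regimen and the treatment-free follow-up.

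**The concern.** An AE count compares groups fairly only if the same finding is recorded in the same way in each group. Here one of the recording routes runs through a decision about study drug, and the decision rules are stricter for GS-9992 than for TAF. The study is open label. The difference acts while GS-9992 is being given, which lies inside the primary safety window (through four weeks after the last GS-9992 dose in Protocol 8.6; 30 days in SAP 7.1.5.1).

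The stakes come from the setting. Safety and tolerability of the 12-week regimens is a primary objective. Protocol 1.4.1 names the liver as the only target organ in the preclinical toxicology. Group 2 is the only TAF-alone control and has about 10 subjects, so one subject is 10% of it. Any distortion runs one way: more hepatic TEAEs with GS-9992 than with TAF alone at equal ALT values.

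**Working it through.** **1. The action rules side by side (confirmed findings)**

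| Finding | GS-9992, Table 7-1 | TAF, Table 7-2 | Can recording differ through drug action? |
|---|---|---|---|
| ALT >2×baseline and 5 to <10×ULN, no hepatic toxicity | Continue | No row | No |
| ALT ≥10×ULN, no hepatic toxicity | Halving or stopping is discussed | Continue; stopping discussed only if persistent | Yes, if GS-9992 is interrupted or stopped; not if it is only reduced |
| ALT >2×nadir, <10×ULN, with hepatic toxicity | Permanent stop | No row | Yes |
| ALT >2×nadir, ≥10×ULN, with hepatic toxicity | Permanent stop | Stopping is discussed | Yes, if TAF is continued |

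Table 7-1 applies to every group receiving GS-9992, so Group 4 is affected as well as Groups 1, 3 and 5.

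**2. Does another rule restore symmetry?** Protocol 7.6.3 has study drug, TAF included, permanently discontinued for a confirmed, clinically significant, related Grade 4 laboratory abnormality. Appendix 3 makes ALT >10×ULN Grade 4, and 7.6.3 has no ALT exception, whereas 7.6.2 and 6.11 do. The text after Table 7-2 gives 6.11 precedence over the general guidelines and also says the more conservative criterion applies. Sites could read this either way, so symmetry is not assured.

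**3. Scale of the ≥10×ULN row.** The plan states no figure on this point, and the sample size has no power calculation (Protocol 8.9, SAP 1.3). For scale only, assume one true rate p in all groups and take three rates from Protocol Section 1:

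- 5/866 = 0.6%: TAF Phase 3, ALT >2×baseline and >10×ULN confirmed at two consecutive visits
- 18/859 = 2.1%: TAF Phase 3, Grade 4 ALT as worst value (Table 1-7)
- 1/16 = 6.3%: earlier GS-9992 Phase 2 trial, 50 mg cohort

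Expected subjects = n × p. Chance of at least one = 1 − (1 − p)^n.

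| | p = 0.6% | p = 2.1% | p = 6.3% |
|---|---|---|---|
| One group of 30: expected | 0.17 | 0.63 | 1.88 |
| One group of 30: chance of ≥1 | 16% | 47% | 86% |
| Groups 1 + 3 + 5 (n = 90): expected | 0.52 | 1.89 | 5.62 |
| Group 2 (n = 10): expected | 0.06 | 0.21 | 0.62 |
| Group 2 (n = 10): chance of ≥1 | 6% | 19% | 48% |

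For example, 90 × 5/866 = 0.52, and 1 − (1 − 1/16)^10 = 0.48.

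These are ceilings for this row at each rate, because only elevations that lead to interruption or discontinuation of GS-9992 become AEs through it. The documents give no rate for the hepatic-toxicity row, so that part cannot be sized.

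**4. What the laboratory tables cover.** Graded ALT by group for the 12 Week Regimen does not depend on drug action. The ALT-flare summary is not planned for that regimen. SAP 7.2.3.1 also leaves Group 4 out of the treatment-emergent 48-week analysis, so as written Group 4 has no treatment-emergent ALT-flare summary.

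**The case against.** The strongest case against acting has five parts.

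- **The limiting phrase in 7.5.** Recording applies to abnormalities independent of the underlying condition, and Protocol 1.4.1 attributes enzyme changes on GS-9992 to immune flares of HBV infection. A site might record no AE even when GS-9992 is stopped. This stands as a source of uncertainty, but it does not make recording neutral between groups.
- **A control subject with an ALT AE and no drug action.** In the earlier trial's 50 mg cohort, 1 of 4 placebo subjects had ALT and AST elevations reported as TEAEs, with no dose modification. So drug action is not needed for an AE. However, that trial treated ALT flares as AEs of special interest, in placebo as well as active subjects. It therefore does not show what 7.5 would yield here.
- **Existing tables.** Graded ALT by group is already planned for 12 weeks, and ALT terms will be visible by preferred term. This stands and limits the harm. It does not correct the TEAE totals.
- **Descriptive design.** No hypothesis is tested, and Groups 3 and 5 are not randomised against Group 2. This also stands and lowers the weight of any such comparison.
- **Timing.** SAP 6.4 reports that GS-9992 development has stopped, so a protocol change helps only recording still to come. The SAP changes do not depend on that.

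A reader might also infer from the TAF Phase 3 data how often high ALT goes unrecorded when TAF is continued: 70 subjects had Grade 3 or 4 ALT (52 + 18), 5 had a Grade 3 increased-ALT AE, and "No subjects in either group had a Grade 4 AE". That leaves 65 of 70 (93%) unmatched. The documents do not support using this ratio here. The recording rules of those studies are not given, and an AE could have been recorded at a lower grade.

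**Conclusion.** The point holds in a limited form. For confirmed ALT ≥10×ULN without hepatic toxicity, and for ALT >2×nadir with hepatic toxicity, the same asymptomatic finding can be a mandatory TEAE in Groups 1, 3, 4 and 5 during GS-9992 dosing and not in Group 2.

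Three stronger readings are tempting, and the documents do not support them:

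- That an ALT abnormality becomes an AE only when drug is stopped. Intervention and signs or symptoms are routes in every group.
- That the tables stop GS-9992 on an ALT value at which they continue TAF. The row facing continued TAF is a discussion that may end in a dose reduction, which is not a recording route. The mandatory stop needs a bilirubin, INR or albumin change as well.
- That Grade 3 or higher TEAEs are inflated. Protocol 7.5 grades such AEs on clinical severity, which need not match the laboratory grade, so this is possible but not certain.

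The expected effect is small: at most about 0.5 to 5.6 of 90 GS-9992 + TAF subjects through the ≥10×ULN row, with a 6% to 48% chance of at least one such value in Group 2. This assumes an equal true rate of 0.6% to 6.3% and adherence to Tables 7-1 and 7-2. The top rate rests on one subject. The case for acting is that the bias has a known direction and is cheap to remove.

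**What to change.** 1. **Protocol 7.5 and the eCRF guidelines.** State that a confirmed on-treatment ALT flare is recorded as an AE in every group, whatever is done with study drug. Use one unambiguous definition, such as the flare definition in SAP 7.2.4 (ALT >2×baseline and ≥5×ULN) with a single stated ULN. The Protocol 7.6 trigger is less suitable because its nadir limb can be read with or without the 5×ULN floor. To cover the second finding below 5×ULN, the sentence should also take in ALT >2×nadir with the listed hepatic-toxicity criteria, again in every group. This changes recording only, not care.
2. **SAP 7.1.6.** Repeat the all-TEAE, Grade 3 or higher and treatment-related summaries without laboratory-only ALT/AST terms. State that between-group comparisons of ALT rest on central-laboratory values.
3. **SAP 7.2.4.** Produce the liver and ALT-flare summary for the 12 Week Regimen, Group 4 included.
4. **Reconciliation by the sponsor.** Table 7-2 and Section 7.6.3 conflict on TAF for a related Grade 4 ALT without hepatic toxicity. The TAF threshold with hepatic toxicity is >10×ULN in the synopsis and ≥10×ULN in Table 7-2.

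Cost: a few more AE entries, some of them in the TAF-alone group, and one extra set of tables. No new tests, visits or subjects are needed. Items 2 and 3 use data already planned for collection, and SAP Section 1 says the SAP is finalised before the final analysis.
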